### 13.8 Subject Confidentiality

Every effort will be made to keep all subject identities confidential. All reports and communications submitted to the Sponsor will be identified only by the subject's initials and subject number. The identity of an individual subject may not be disclosed in any publication relating to this study.

In connection with this study, representatives of Health Canada, or other regulatory bodies outside of Canada, such as the United States Food and Drug Administration representatives of the local IRB may, in certain circumstances, review study source documentation including subject medical records.

### 13.9 Monitoring

In accordance with good clinical practices, the study will be monitored by Sponsor representatives. These representatives will have access to and will review source documents relating to this study, including subject medical records.

The status of drug storage, dispensing, and accountability will also be assessed during periodic visits.

At any time, each site may be audited either by Boston Biomedical personnel, or by a contractor acting on behalf of Boston Biomedical, or by a regulatory agency such as the FDA or Health Canada.

### 13.10 Case Report Form (CRF) Completion

A set of CRFs will be provided for each study subject. All forms must be filled out in non-erasable ink or typed. The Investigator will sign and date each CRF as indicated. Correction of data on a CRF will be made by crossing out the incorrect data in a manner that leaves the previous entry legible and writing the correct information next to the crossed out entry. "White-out" and erasures are not permitted. Each correction must be initialed and dated by the individual making the correction. After the CRFs have been collected by Boston Biomedical, all corrections will be made via a query resolution form, and no further corrections should be made on the site's copy of the CRF.

### 13.11 Final Site Report

The Principal Investigator or associate must notify the IRB when the study is closed and provide a final report to the IRB within 90 days of the last subject's completion of the study. A copy of this final report must also be provided to Boston Biomedical.

### 13.12 Final Study Report

At the conclusion of the study, after the data are analyzed, Boston Biomedical will prepare a final study report. A copy of this report will be provided to the Principal Investigator at each center.

The preparation of the final study report may be delegated to a contract research organization.

### 13.13 Use of Information

All personal information pertaining to subjects in this study and in any subsequent reports will be kept confidential. Subjects will be identified only by their initials and by a subject number. It is the responsibility of the Investigator to keep a subject listing for cross-referencing.

The Investigator understands that the information developed in the clinical study will be used by Boston Biomedical in connection with the development of the study drug. This information may be disclosed to other clinical investigators, the FDA, Health Canada and other government agencies.

All information disclosed to the Investigator(s) by Boston Biomedical for the purpose of having the Investigator(s) conduct the clinical trial described in this protocol or generated by the Investigator(s) as results in the clinical trial shall be treated by the Investigator(s) as strictly confidential. The Investigator(s) shall not use such information other than for the purpose of conducting the clinical trial and may not disclose such information to others, except when such disclosure is to colleagues and/or employees who reasonably require the information to assist in carrying out the clinical trial and who are bound by like obligations of confidentiality. Notwithstanding, the Investigator(s) may use or disclose to others any information which: (i) was known to the Investigator(s) prior to the date of its disclosure, (ii) is now, or becomes in the future, publicly available; or (iii) is lawfully disclosed to the Investigator(s) on a non-confidential basis by a third party who is not obligated to Boston Biomedical or any other party to retain such information in confidence.

### 13.14 Publication

Boston Biomedical acknowledges that the Investigator(s) have certain professional responsibilities to report to the scientific community on findings in clinical investigations they conduct. The Principal Investigator shall have the right to publish the results of research performed under this protocol, provided such publication does not disclose any Confidential Information or trade secrets of Boston Biomedical (other than the Clinical Data). If the Study is conducted as part of a multi-center protocol, Principal Investigator agrees not to independently publish their findings except as part of an overall multi-center publication, unless specifically approved in writing by Boston Biomedical. The Principal Investigator agrees to, prior to submitting a manuscript, abstract, or any other written or oral presentation describing the Data for publication or presentation, forward to Boston Biomedical a copy of the item to be submitted for publication or presentation. Upon reasonable request by Boston

Biomedical within 30 days of receipt, the Principal Investigator agrees to withhold such publication an additional 60 days to permit the preparation and filing of related patent applications. In addition, Boston Biomedical shall have the right to require the Principal Investigator to delete from any publication or presentation any Confidential Information (other than the Clinical Data) of Boston Biomedical's and to require that any publication or presentation concerning the Study acknowledge the Sponsor's support.

### 13.15 Research Outside the Terms of this Protocol

Boston Biomedical has a legal responsibility to report fully to the regulatory authorities all the results of administration of its investigational drugs.

No investigative procedures other than those described in this protocol shall be undertaken on subjects enrolled in this study (unless required for the care of the subject), without the agreement of the IRB/Ethics Committee and Boston Biomedical. The nature and results of any such procedures must be recorded and reported by a method agreed between Boston Biomedical and the Investigator. The consent of the subjects must be obtained before any such procedures are undertaken.

The investigative drug provided to the Investigator for use under this protocol may not be used for any other purpose, including another study, compassionate use, or personal use.

# 14 APPENDIX A: SCHEDULE OF ASSESSMENTS

### BBI608 + Cetuximab

lv Visit			om last dose																				
End of Study Visit			≤30 days from last BBI608 dose			X		X	×	X	X	X	X	X	X	X	X		$\mathbf{X}^{7}$	X	X		
	pu	4	26																				•
	Cycle 2 & Beyond	3	19	± 1 day																			>
	ycle 2 &	2	12	# 1																			>
ns 	С	1	S.			×		×	×	×	×	×	×	×		×				X	X	X	>
Study Evaluations 		4	26					×	×	×	×	×	×	×				×		X	X	×	×
udy Ev		3	19					×	×	×	×	×	×	×						X	X	×	×
St	Cycle 1	2	12	± 1 day				X	×	×	X	×	×							X	X	X	×
	Cy		∞	#													X						
		1	S					×	×	×	×	×	×	×				X		X	X	X	×
			1												×							X	
Pre-Study	Evaluation	0	0	-7 ± 3 days	X	×	X	X	×	X	X	X	X	X	X	X	X		$X^6$	X			
Tests & Procedures		Week	Day	Window	Medical history	Physical examination	Serum pregnancy test 	Karnofsky performance status	Vital signs, Weight	Hematology 	Blood chemistry 	Liver function tests 	Electrolytes 	Urinalysis 	12-Lead electrocardiogram	Tumor markers 	Tumor biopsy 	Pharmacokinetics (first 6 patients only)	Tumor measurement & staging 	Concomitant medications	Adverse events 	Dispense BBI608	Cetuximah infusion

<sup>1 Calculated from the date of first BBI608 dose.
 Refer to Section 6.3 for description of laboratory assessments.
 If applicable

<sup>4 Including tumor measurements, following RECIST 1.1.
 Prior to cycle 3 and every other cycle thereafter, assessments must be made utilizing the same imaging method as baseline

<sup>6. Unless CT/MRI has been performed within last three weeks . Unless CT/MRI has been performed within last four weeks. . Patients will be followed until resolution of any drug-related AE or SAE occurring during the study or within 30 days of last BBI608 administration.

## BBI608 + Panitumumab

End of Study Visit	•		≤30 days from last BBI608 dose			X		X	X	X	X	X	X	X	X	X	X		$\mathbf{X}^7$	X	X		
	pu	4	22																				X
	z Beyon	3	15	day																			
ıSı	Cycle 2 & Beyond	2	∞	± 1 day		×		X	X	X	X	X	X	X		X				X	X	X	X
aluatior	Ď	1	1																				
Study Evaluations		4	22					X	X	X	X	X	X	X				X		X	X	X	X
Str	le 1	3	15	day																			
	Cycle 1	2	∞	± 1 day				X	X	X	X	X	X	X			X	X		X	X	X	X
		1	1												X							X	
Pre-Study	Evaluation	0	0	-7 ± 3 days	X	X	X	X	X	X	X	X	X	X	X	X	X		$X^6$	×			
Tests & Procedures		Week	Day	Window	Medical history	Physical examination	Serum pregnancy test 	Karnofsky performance status	Vital signs, Weight	Hematology 	Blood chemistry 	Liver function tests 	Electrolytes 	Urinalysis²	12-Lead electrocardiogram	Tumor markers 	Tumor biopsy 	Pharmacokinetics (first 6 patients only)	Tumor measurement & staging 	Concomitant medications	Adverse events 	Dispense BBI608	Panitumumab infusion

Confidential

Calculated from the date of first BBI608 dose. Refer to Section 6.3 for description of laboratory assessments.

Ifapplicable

Including tumor measurements, following RECIST 1.1.

Prior to cycle 3 and every other cycle thereafter, assessments must be made utilizing the same imaging method as baseline Unless CT/MRI has been performed within last three weeks.

Unless CT/MRI has been performed within last four weeks.

Patients will be followed until resolution of any drug-related AE or SAE occurring during the study or within 30 days of last BBI608 administration.

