## 5.5 End of Study Evaluation

All patients will be followed for a minimum of 30 days after the last dose of BBI608. If a patient is removed from the study due to drug-related adverse events, the patient will be followed until resolution of any drug-related AE occurring during the study or within 30 days of the last BBI608 dose, or for 30 days, whichever is longer. In the presence of toxic effects, follow-up visits will be required every four weeks until all study related toxicities have resolved to baseline (or < Common Terminology Criteria for Adverse Events [CTCAE] Grade 1), stabilized or are deemed irreversible.

The following assessments will be made during the end of study visit:

- Physical examination
- Karnofsky performance status
- Vital signs (weight, temperature, blood pressure, respiration and pulse)
- Hematology (see Section 6.3)
- Blood chemistry (see Section 6.3)
- Liver function tests (see Section 6.3)
- Electrolytes (see Section 6.3)
- Urinalysis (see Section 6.3)
- 12-lead ECG
- Tumor marker, if applicable
- Tumor biopsy, if applicable (see Section 6.5.1)
- Tumor measurement and staging
- Assess adverse events
- Record concomitant medications

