### 8 SAFETY ASSESSMENTS

### 8.1 Adverse Events

## 8.1.1 Assessments

The Investigator is responsible for monitoring the safety of patients who have enrolled in the study. All AEs considered to be related to BBI608 occurring after any administration of the study drug will be followed until the event resolves. AEs will be evaluated using the National Cancer Institute (NCI) CTCAE, Version 4.0, published 28 May 2009.

Investigators are required to document all AEs occurring during the clinical trial, commencing with the first dose of BBI608 and including the protocol-defined post-treatment follow-up period (21 Code of Federal Regulations [CFR] §312.64[b]) on designated CRF pages. AEs occurring following the signature of the informed consent, but prior to the first dose of study drug will not be reported as AEs. It is also important to record all AEs that result in permanent discontinuation of the investigational product being studied, whether serious or non-serious.

Serious adverse events (SAEs), as defined below, must be reported to Boston Biomedical Inc. or its representative within 24 hours of knowledge of their occurrence.

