### 10.7 Safety Analysis

Safety will be assessed by physical examination, and laboratory assessments. Adverse events will be graded according to the NCI CTCAE, version 4.0. The incidence of adverse events and DLTs will be evaluated for each combination arm, and for all patients combined. Patients will be followed for adverse events for at least 30 days after the last dose of BBI608, or until recovered from all related BBI608 adverse events.

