8.2.4.1. Adverse Events

Overall Summary of AEs

An AE will be regarded as treatment-emergent, if

- it occurs on the day of or after the first dose of either napabucasin or a combination drug and up to 30 days after the last dose of any study drug; or
- it occurs prior to first dose date of either napabucasin or a combination drug and worsens in severity on therapy and up to 30 days after the last dose of study drug.

Adverse events will be coded by SOC and PT using the MedDRA version 18.0 prior to the analysis. The severity of AEs will be graded by the investigator using CTCAE Version 4.0. The verbatim term will be included in the AE listings.

An overview of treatment-emergent adverse events (TEAEs) will be provided. The number and percentage of patients will be summarized for:

- Patients with at least one TEAE
- Patients with TEAE of CTCAE Grade 3 or higher
- Patients with serious TEAE
- Patients with napabucasin related TEAE
- Patients with napabucasin related TEAE of CTCAE Grade 3 or higher
- Patients with Cetuximab related TEAE
- Patients with Cetuximab related TEAE of CTCAE Grade 3 or higher
- Patients with Panitumumab related TEAE
- Patients with Panitumumab related TEAE of CTCAE Grade 3 or higher
- Patients with Capecitabine related TEAE
- Patients with Capecitabine related TEAE of CTCAE Grade 3 or higher
- Patients with napabucasin related serious TEAE
- Patients with napabucasin related serious TEAE of CTCAE Grade 3 or higher
- Patients with Cetuximab related serious TEAE
- Patients with Cetuximab related serious TEAE of CTCAE Grade 3 or higher
- Patients with Panitumumab related serious TEAE
- Patients with Panitumumab related serious TEAE of CTCAE Grade 3 or higher
- Patients with Capecitabine related serious TEAE
- Patients with Capecitabine related serious TEAE of CTCAE Grade 3 or higher
- TEAE as the primary reason leading to end of study

Summary of AEs by System Organ Class and Preferred Term

The number and percentage of patients with AEs by SOC and PT and maximum CTCAE grade will be summarized. A summary of TEAEs of CTCAE grade 3 or higher (Grade 3, 4, 5) will be presented by SOC and PT and maximum CTCAE grade. A summary of TEAEs by PT and maximum grade will be presented in the descending order of frequency counts for all grades.

Treatment Related TEAE

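### Appendix A lets the end-of-study visit fall any time up to Day 30 after the last BBI608 dose, so patients without toxicity may have no scheduled adverse-event contact for the rest of the 30-day safety window

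*Protocol*

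**What the plan says.** **The visit.** The Appendix A schedules for cetuximab, panitumumab and capecitabine give the end-of-study visit the same window: "≤30 days from last BBI608 dose". It is the last column with a mark in the adverse-event row.

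**The follow-up period.** Protocol 5.5 opens: "All patients will be followed for a minimum of 30 days after the last dose of BBI608". Protocol 10.7 says: "Patients will be followed for adverse events for at least 30 days after the last dose of BBI608, or until recovered" from related events. Footnote 8 of the schedules adds: "Patients will be followed until resolution of any drug-related AE or SAE occurring during the study or within 30 days of last BBI608 administration". Protocol 8.1.1 has investigators record adverse events from the first BBI608 dose onward, "including the protocol-defined post-treatment follow-up period".

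**Later visits.** When toxic effects are present, Protocol 5.5 states that "follow-up visits will be required every four weeks until all study related toxicities have resolved to baseline" or to a low grade, have stabilized, or are judged irreversible. No other visit or call after the end-of-study visit is scheduled for adverse events.

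**The analysis window.** SAP 8.2.4.1 treats an event as treatment-emergent if it occurs on or after the first dose and "up to 30 days after the last dose of any study drug". The same section summarizes deaths within 30 days of the last dose of any study treatment. It cuts off ongoing Grade II or above diarrhea at data cutoff or, if earlier, at a safety follow-up completion date, defined as last treatment plus 30 days or death.

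**The concern.** The schedule sets a maximum where the follow-up text sets a minimum. A site that sees a patient five days after the last dose has complied with Appendix A. If that patient has no toxicity, the protocol names no further occasion on which anyone asks about adverse events.

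Early visits are plausible. Under Protocol 5.4, documented progression ends treatment and the patient may then start any other therapy. The end-of-study visit also includes tumor measurement unless a scan was done in the previous four weeks. Both give a site reason to book the visit soon after the last dose.

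Safety is a primary objective. The SAP's windows presume that each patient is observed through Day 30. If observation in practice ends with the visit, its length varies between patients and sites, and event counts partly reflect booking habits. The exposure is greatest for new, non-serious events that begin after the visit.

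**Working it through.** The plan states no figure on this point, so there is none to reproduce. The check compares time windows.

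**Inputs**
- Visit day *d*, counted from the last BBI608 dose: 0 ≤ *d* ≤ 30 (Appendix A, all arms).
- Required follow-up: at least 30 days from the last BBI608 dose (Protocol 5.5 and 10.7).
- Visits when toxicity is present: every four weeks, so the next falls at about *d* + 28 (Protocol 5.5).
- SAP counting window: through 30 days after the last dose of any study drug (SAP 8.2.4.1).
- *L*: days by which the last combination-drug dose follows the last BBI608 dose, and zero if it does not. The documents do not give *L*; 0 to 14 days is assumed.

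**Step 1: days after the visit, counted from BBI608.** Days remaining = 30 − *d*; share of calendar days = (30 − *d*)/30.

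| Visit day *d* | 30 − *d* | Share of 30 days | Next visit if toxicity present (*d* + 28) |
|---|---|---|---|
| 0 | 30 | 100% | 28 |
| 7 | 23 | 77% | 35 |
| 14 | 16 | 53% | 42 |
| 21 | 9 | 30% | 49 |
| 28 | 2 | 7% | 56 |
| 30 | 0 | 0% | 58 |

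Only a visit on exactly Day 30 both satisfies the schedule and closes the 30-day minimum.

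**Step 2: who is affected.** With toxicity at the visit, the next visit reaches Day 30 when *d* + 28 ≥ 30, that is, when *d* ≥ 2. The gap therefore falls mainly on patients without toxicity at the visit and on events that begin after it.

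**Step 3: the SAP window.** This window ends on Day 30 + *L*, so the days after the visit are 30 + *L* − *d*. For a Day 30 visit the remainder is *L*: 0, 7 or 14 days for *L* = 0, 7 or 14. For a Day 7 visit it is 23, 30 or 37 days. Even a visit at the limit of the schedule can fall short of the SAP window if the combination drug is stopped after BBI608.

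**Step 4: whether other text supplies a contact.** Protocol 8.1.1 sets the recording period, and footnote 8 sets how long a drug-related event is followed. Neither names an occasion for finding a new event. Protocol 8.1.2 ties the investigator's assessment to visits and otherwise relies on patients being told to report events. For a patient without toxicity, the period after an early visit rests on that reporting.

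**The case against.** The strongest reply is that a limit on the visit is not a limit on follow-up. Protocol 5.5 states the follow-up duty first and lists the visit procedures separately. A site can hold the visit by Day 30 and still follow the patient to Day 30. Protocol 8.1.1, 8.1.2 and footnote 8 keep the duty to record and report alive whatever the visit date. This stands: what is missing is a dated contact, not the obligation. It does not remove the gap, because for patients without toxicity no contact is named to discharge that obligation.

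Four stronger readings are tempting, and the documents do not support them.

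- *That the SAP itself demands at least 30 days.* It sets an upper limit on what is counted. It needs data through Day 30 but does not contradict the visit window.
- *That every patient who stops treatment is exposed.* Patients with toxicity have four-weekly visits, and a patient seen on Day 30 has no gap in the BBI608-based window.
- *That 30-day deaths are under-counted.* Protocol 8.2.2 requires serious events, including death from any cause, to be reported within 24 hours. Overall survival is a secondary endpoint, and SAP Appendix 1.3 draws on a survival follow-up form.
- *That the percentages estimate lost events.* They are shares of calendar days. The documents give neither actual visit timing nor the rate of late events.

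The point also rests on one sign in the schedule heading. It reads the same in all three schedules, but should be confirmed on the page.

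**Conclusion.** The mismatch is real and worth correcting. Appendix A allows a visit at which scheduled adverse-event assessment ends before the 30 days required by Protocol 5.5 and 10.7, and before the end of the SAP's counting window. For patients without toxicity at an early visit, new events afterwards depend on unscheduled reporting. These are mainly non-serious events, and they can be under-counted to a degree that varies with visit timing.

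The uncovered period ranges from 0 to 30 days on the BBI608 clock. It is longer by *L* on the SAP clock, where *L* of 0 to 14 days is an assumption. How many events would be missed cannot be derived from the documents. The conclusion assumes that no contact schedule exists outside the protocol and SAP, and that some visits take place before Day 30.

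**What to change.** Reconcile Appendix A (all three schedules) with Protocol 5.5, 10.7 and SAP 8.2.4.1 in one of two ways.

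1. Keep the early visit for scan and laboratory tests, and add a telephone contact for adverse events and vital status on or shortly after Day 30 from the last dose of any study drug. The cost is one call per patient.
2. Reset the visit window to Day 30 or later. This is only a heading edit in three tables, but end-of-study tests may then fall after new therapy has begun.

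The first option avoids that drawback. In either case, state one reference dose: Protocol 5.5 and 10.7 count from BBI608, the SAP from any study drug. If the window stays tied to BBI608, up to *L* days of the SAP window can remain uncovered.

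If visits are already complete, tabulate by arm the days from last dose to last adverse-event assessment, so that readers can see how much of the 30-day window was observed. This needs only dates of dosing and assessment.

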## 5.2 Pre-Study Evaluations (Baseline) (1 week ±3 days prior to the first dose of BBI608\*)

After written informed consent is obtained according to ICH-GCP and local regulations, the patient will be evaluated for inclusion and exclusion criteria according to the eligibility criteria listed in Section 3.

The following will be evaluated and documented within seven days prior to first dose of BBI608:

- Medical history
- Physical examination

- Karnofsky performance status (see Section 15)
- Vital signs (weight, temperature, blood pressure, height, respiration and pulse)
- Hematology (see Section 6.3)
- Blood chemistry (see Section 6.3)
- Liver function tests (see Section 6.3)
- Electrolytes (see Section 6.3)
- Urinalysis (see Section 6.3)
- Serum pregnancy test (if applicable)
- Tumor markers if applicable
- Tumor biopsy, if applicable (see Section 6.5.1)
- 12-lead electrocardiogram (ECG)
- Tumor measurement and staging[computed tomography (CT) or magnetic resonance imaging (MRI) acceptable] \*

\*All CT and MRI scans can be used as the baseline assessment if they were performed within three weeks prior to the first scheduled dose of BBI608.

Archival tissue samples from a prior biopsy or surgery should be collected from all patients enrolled in the clinical trial if they are available (See Section 17: Appendix E).

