6.3. Response Evaluable Set

The response evaluable set is defined as patients who have received at least one cycle of study treatment unless discontinued early due to death or PD and have had at least one disease assessment following the initiation of therapy. At least one cycle of study treatment is defined as at least 80% daily treatment compliance at targeted dose level during one cycle (cycle 1 or cycle 2) period prior to the first post-dosing imaging assessment. The response evaluable set will be used for analyses of disease control rate and overall response.

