7.2. Definition of Baseline Values

Unless otherwise specified, the baseline value is defined as the value collected at the time closest to, but on or prior to, the start of study drug administration. CT and MRI scans may be considered for baseline assessment only if they were performed within 30 days of the first dose of napabucasin.

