Appendix 1.3. Censoring for Time to Event Data

Table A.1.3.1 summarizes the censoring rules for the PFS analysis and displays censoring hierarchy for this study. Table A.1.3.2 shows the general reasons for PFS censoring and where the censoring hierarchy in Table A.1.3.1 came from.

Table A.1.3.1 PFS Censoring Reasons and Hierarchy

Censoring Hierarchy	Situation	Date of Event or Censor	Event / Censor
1	No baseline radiological tumor assessment available	Date of First Dose	Censored
2	New anticancer treatment started and no tumor progression	Date of previous adequate radiological assessment immediately prior to start of new therapy	Censored
3	Tumor progression (per RECIST 1.1) documented after 2 scan intervals following previous adequate radiological tumor assessment	Date of previous adequate radiological assessment	Censored
4, 5	No tumor progression (per RECIST 1.1) and patient lost to follow-up or withdrawal of consent	Date of last adequate radiological Assessment	Censored
6	No post baseline radiological tumor assessment available and no death reported within 2 scan intervals following the date of the first dose of study drug (napabucasin)	Date of First Dose	Censored
	No post baseline radiological tumor assessment available but death reported within 2 scan intervals following the date of the first dose of study drug (napabucasin)	Date of Death	Event
7	No tumor progression (per RECIST 1.1) and no death reported within 2 scan intervals following last adequate radiological tumor assessment	Date of last adequate radiological tumor assessment	Censored
	No tumor progression (per RECIST 1.1) but death reported within 2 scan intervals	Date of death	Event

following last adequate radiological tumor assessment		
Tumor progression (per RECIST 1.1) documented within 2 scan intervals following previous adequate radiological tumor assessment	Earliest of the target, non- target and new tumor assessment dates	Event

Notes: (1) Symptomatic deteriorations (ie, symptomatic progressions, which are not radiographically confirmed) will not be considered as progressions.

(2) If target, non-target and new lesion assessments have different dates within a visit, then the earliest of those dates will be considered as the date of the tumor assessment if the assessment for that visit is progressive disease (PD); otherwise the latest date will be used.

(3) Adequate radiographical tumor assessment refers to an assessment with overall response of CR, PR, SD, or PD.

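### The end-of-study scan waiver can be met by the baseline scan, so an early clinical progressor may have no post-baseline assessment, fall outside the primary DCR set and be censored for PFS at first dose

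*Protocol*

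**What the plan says.** **End-of-study scan.** Protocol 5.5 lists "Tumor measurement and staging" among the end-of-study assessments, with no exception. In Appendix A the same item carries footnote 7 in the cetuximab, panitumumab and capecitabine schedules: "Unless CT/MRI has been performed within last four weeks". The schedules time the visit at "≤30 days from last BBI608 dose".

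**Baseline scan.** Protocol 5.2 accepts scans "if they were performed within three weeks prior to the first scheduled dose of BBI608". SAP 7.2 is wider and accepts them "only if they were performed within 30 days of the first dose of napabucasin".

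**On-study scans.** Protocol 5.4 sets eight-week intervals, with earlier imaging if clinically indicated. Appendix A footnote 5 places the first scan before cycle 3. Protocol 5.6 allows removal for clinical progression as well as radiologic progression.

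**DCR.** SAP 6.3 requires one cycle of treatment "unless discontinued early due to death or PD and have had at least one disease assessment following the initiation of therapy". Protocol 10.3 requires a cycle and an assessment, and 10.4 requires 80% of a cycle. Neither has a PD exemption. SAP 8.2.2 adds a DCR sensitivity analysis in the whole safety set.

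**PFS.** SAP 8.2.3.3 analyses the safety set. Row 6 of Table A.1.3.1 censors at first dose in this case: "No post baseline radiological tumor assessment available and no death reported within 2 scan intervals". If a death is reported in that interval, it is an event. Note 1 to the table says that symptomatic deterioration without radiographic confirmation is not progression.

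**The concern.** The natural purpose of footnote 7 is to spare a patient a repeat of a recent on-study scan. As worded it also spares a patient whose only recent scan was the baseline one. For the first eight weeks no on-study scan is scheduled, so for someone who leaves in the first weeks the end-of-study scan may be the only chance of a post-baseline assessment.

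The patients affected are not a random subset. SAP 6.3 lifts the one-cycle rule for early death and PD, evidently so that early failures stay in the denominator, but it keeps the requirement for a post-baseline assessment. A waived scan therefore undoes the exemption for the patients it was written for. The same missing scan removes the only evidence that could make their progression a PFS event. If such patients exist, primary DCR and PFS both look better than they should.

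**Working it through.** The plan states no figure on this point, so there is none to reproduce. The check is date arithmetic, followed by a denominator calculation.

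**1. When can the baseline scan trigger the waiver?** For a scan *s* days before first dose, the visit must be no more than 28 days after the scan. The latest waived visit is 28 − *s* days after first dose.

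| Baseline scan | Latest waived visit (days after first dose) |
|---|---|
| day −1 | 28 − 1 = 27 |
| day −7 | 28 − 7 = 21 |
| day −14 | 28 − 14 = 14 |
| day −21 (Protocol 5.2 limit) | 28 − 21 = 7 |
| day −28 to −30 (SAP 7.2 only) | 0 or less: no waiver after first dose |

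Example: with a scan on day −5 and a visit on day 18, the scan is 5 + 18 = 23 days old and the visit scan is waived. If that visit takes place on day 24 or later, 5 + 24 = 29 days exceeds 28 and footnote 7 requires the scan.

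**2. Who leaves the DCR set because of the waiver?** Eighty per cent of a 28-day cycle is 0.80 × 28 = 22.4 days. Nearly all patients who stop inside the window for toxicity or withdrawal fail the one-cycle rule with or without a scan. Only the group that SAP 6.3 exempts, mainly early progressors, is excluded by the missing scan itself.

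**3. What could the missing scan have shown?** Under SAP Appendix 1.2, progression within 16 weeks plus one day gives a best response of PD. SD before 8 weeks minus one day is classed NE. An early scan can therefore not be credited as SD. Unless it showed CR or PR, it could not add disease control.

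**4. Size for DCR.** Let *N* be the number treated, *D* the number with disease control and *k* the early progressors left without a scan. Primary DCR is *D*/(*N* − *k*), against *D*/*N* had each scan been done and shown PD. The documents give no value for *k* and no observed DCR, so *k* = 1 to 3 and a DCR of 50% are assumptions. *N* = 24 is the Simon total for the cetuximab and panitumumab arms. *N* = 50 is the expansion limit.

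| *k* | 12/(24 − *k*) | 25/(50 − *k*) |
|---|---|---|
| 0 | 50.0% | 50.0% |
| 1 | 12/23 = 52.2% | 25/49 = 51.0% |
| 2 | 12/22 = 54.5% | 25/48 = 52.1% |
| 3 | 12/21 = 57.1% | 25/47 = 53.2% |

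For scale, the exact 95% interval is 29.1% to 70.9% for 12/24 and 35.5% to 64.5% for 25/50.

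**5. PFS.** Two scan intervals are 2 × 8 = 16 weeks. A patient with no post-baseline scan and no death in that time is censored at day 0 and leaves the risk set before any event can occur. With three such patients among 24, the Kaplan-Meier curve rests in effect on 24 − 3 = 21. A death within 16 weeks is counted, subject to one limit: new anticancer therapy without documented progression ranks second in the censoring hierarchy, above row 6, so a patient who moves on to other treatment is censored first.

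**The case against.** Much of the case on the other side stands.

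- **PFS.** A reader might infer that these patients drop out of PFS altogether. They do not. They belong to the safety set on which PFS is summarised, and an early death can count as an event. What is lost is the date of a progression that was never imaged.
- **A safeguard exists for DCR.** The safety-set sensitivity analysis covers all treated patients, so a gap between the two estimates would show. It does not change the primary estimate, and it cannot recover a progression that no scan recorded. The PFS sensitivity analysis in SAP 8.2.3.3 changes only the population and the start date, so it does not help here.
- **The waiver is not the general cause of exclusion.** A reader might blame it for every early leaver. Under Protocol 10.3 and 10.4 an early leaver fails the cycle rule whatever the scan shows. Under the SAP the same is true of nearly all toxicity and withdrawal cases. The point is confined to early progressors under SAP 6.3.
- **The window is narrow.** The visit must fall within 28 days of the baseline scan but may take place up to 30 days after the last dose, and many visits will be late enough to require the scan. Protocol 5.4 also lets the investigator image earlier.
- **The reading is literal.** Sites may take footnote 7 to mean on-study scans only, or may follow 5.5. That is possible, but the text does not say so, and two sites could properly act differently.
- **The effect is small beside the uncertainty.** SAP 4.1 has no hypothesis test and SAP 4.2.2 says the Simon rule was not applied, so no formal decision turns on a few percentage points. This limits the weight of the point. It does not alter the direction of the bias.

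**Conclusion.** The point holds in a limited form. Footnote 7, followed as written, conflicts with Protocol 5.5 and can leave an early clinical progressor with no post-baseline assessment. That patient is then outside the primary DCR set despite the early-PD exemption in SAP 6.3, and is censored for PFS at first dose unless a death within two scan intervals is counted. The bias favours the treatment in both analyses.

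Its size cannot be known from the documents and is probably small. The range in the working, at most about 7 percentage points for 3 of 24 and about 3 points for 3 of 50, rests on three assumptions: the number of such patients, a DCR of 50%, and every waived scan showing PD. A reader might infer a large distortion of the trial's result, but the documents give no count of affected patients that would support that.

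**What to change.** In footnote 7 of all three schedules, insert *post-baseline* before CT/MRI, so that only a scan taken after the start of treatment can waive the end-of-study scan. Then reconcile 5.5 with the schedules, for example by having it refer to the footnote, so that the two state one rule. No new timing rule is needed. The gap then closes for every patient who attends the visit. It remains for those who do not attend or cannot be scanned.

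The cost is a repeat scan less than four weeks after baseline in a few early leavers, which 5.5 already lists.

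If conduct is too far advanced for a schedule change to matter, report by arm, for the safety set, how many patients stopped early with no post-baseline assessment and why. SAP Appendix 1.2 already has that reason for NE. The count must be made in the safety set, because these patients are by definition absent from the response evaluable set.
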